While numerous studies have investigated the broader implications of health education interventions on vaccination awareness and rates, there remains a distinct lack of focused research specifically targeting primary school students, especially within the context of China.¹⁰⁻¹² The unique age group, characterized by their transitional cognitive abilities and susceptibility to influence, may respond differently to health literacy interventions than other age cohorts. Moreover, regional differences, cultural practices, and local health infrastructure in China might further impact the effectiveness of such interventions. Thus, this study aims to investigate the influence of health education on influenza vaccination rates and the level of influenza vaccination health literacy among fourth and fifth-grade primary school students. The methodological approach will involve a cluster randomized trial with schools serving as the unit of analysis. The findings will provide a scientific basis for future interventions.

METHODS AND ANALYSIS

Study objectives

This study seeks to explore the impact of health education interventions on vaccination and influenza vaccination awareness among senior primary school students. By evaluating the impact of health education on the seasonal influenza vaccination rate and the level of influenza vaccination health literacy, we aim to provide a scientific foundation for regional influenza prevention and control

strategies. The specific objectives of this research are: 1) To ascertain the rate of influenza infection, the status of influenza vaccination, and the level of health literacy related to influenza vaccination among primary school students in Dongguan City. 2) To compare and contrast the influenza vaccination rate and the level of influenza vaccination health literacy between the experimental and control groups, thereby evaluating the impact of health education intervention on these parameters. 3) To assess the efficacy of influenza vaccine immunization among primary school students in Dongguan City.

Study design

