The study employs a multi-stage cluster sampling method. In the first stage, one central urban area (tentatively identified as Dongcheng Street, which oversees 31 primary schools) and one non-central urban area (tentatively identified as Gaobu Town, which oversees 13 primary schools) will be randomly selected, reflecting the urban-rural structure of Dongguan City. In the second stage, ten primary schools will be randomly selected from each administrative district, with five designated as intervention group schools and the remaining five as control group schools. This results in a total of twenty primary schools, evenly split between the intervention and

control groups. In the third stage, two classes from each of the two grades (fourth and fifth grades) are randomly selected from each of the twenty selected schools using a cluster sampling method, with surveys conducted at the class level. Each school comprises a minimum of 152 students. Schools with 152 students will have one additional class randomly selected. The final estimated total sample size is projected to be 3036. Random sampling and randomized grouping are achieved using computer software to generate random numbers. The sample size is determined using the following formula:

$$n = \frac{\left\{ z_{1-\alpha/2} \sqrt{2(m-1)\rho + 2} + z_{\beta} \sqrt{m\rho + 1} \right\}^2 * \{p_1(1-p_1) + p_2(1-p_2)\}}{(p_1 - p_2)^2}$$

where: n is the desired sample size for each cohort, $z_{1-\alpha/2}$ is the value corresponding to the accepted Type I error rate (eg $z_{1-\alpha/2}$ about 1.96 for an error rate of 0.05), z_{β} is the value corresponding to the desired statistical power, e.g., for a power of 0.8, z_{β} is approximately 0.84. m is the size of each cohort, ρ is the intra-group correlation coefficient, p_1 is the expected outcome rate in the test group (ie, influenza vaccination rate), and p_2 is the expected outcome rate in the control group. Based on the assumption that the anticipated influenza vaccination rate is 80% in the intervention group and 50% in the control group, the estimated sample size, denoted as 'n', is 138 students per school.^{13, 14} This implies that approximately 138 primary school students are required for each group, yielding a total sample size of 2760 individuals. To account for potential sample attrition, the sample size is expanded by 10%, resulting in a final estimated total sample size of 3036 for statistical analysis.

Intervention methods

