Primary outcomes include the influenza vaccination rate and the influenza vaccination health literacy level. The influenza vaccination rate will be calculated as the number of vaccinated individuals divided by the total number of individuals, multiplied by 100%. Regarding the influenza vaccination health literacy level, each correct answer for the scale will be scored as one point, with incorrect answers receiving no points. Based on the scores, health literacy levels will be categorized as low, medium, or

high.

Secondary outcomes include influenza incidence, the ILI incidence and the influenza vaccine protection rate. The influenza incidence will be calculated as the number of individuals diagnosed with influenza divided by the total number of individuals, multiplied by 100%, The ILI incidence will be calculated as the number of ILI cases divided by the total number of participants, multiplied by 100%. The influenza vaccine protection rate will be calculated as the difference between the incidence rate in unvaccinated individuals and the incidence rate in vaccinated individuals, divided by the incidence rate in unvaccinated individuals, multiplied by 100%.

Statistical analysis plan

Continuous variables will be described using means \pm standard deviation or median (interquartile range), and comparisons will be made using two independent samples t-tests or Wilcoxon rank-sum tests. Categorical variables will be described using frequency and composition ratios, and rate comparisons will be conducted using Chi-square tests or Fisher's exact probability method. The association between the level of influenza vaccination health literacy and vaccination willingness will be analyzed using multivariate logistic regression.

Quality control

Quality Control will be conducted in accordance with the requisite quality control standards, with dedicated on-site quality control personnel assigned to oversee investigation and evaluation. These personnel should be proficient in various testing technical requirements and quality control points, and familiar with the on-site

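### Schools are randomised, but the SAP compares the student-level vaccination rate by a chi-square or Fisher test that makes no allowance for school, so the nominal 5% error rate fails if schools differ within district

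*Combined protocol and SAP*

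**What the plan says.** The introduction describes "a cluster randomized trial with schools serving as the unit of analysis". Under Sampling method, "ten primary schools will be randomly selected from each administrative district, with five designated as intervention group schools" and the other five as controls, which makes 20 schools and a 5:5 split within each district. The two districts are chosen as "reflecting the urban-rural structure of Dongguan City". Whole classes are then drawn, "with surveys conducted at the class level". The sample-size formula in that section contains an intra-group correlation and a cohort size, but gives a value for neither. It reports 138 students per school, 2760 in total and 3036 after adding 10%.

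Under Study outcomes, "The influenza vaccination rate will be calculated as the number of vaccinated individuals divided by the total number of individuals". Under Statistical analysis plan, "rate comparisons will be conducted using Chi-square tests" or Fisher's exact method. For continuous variables, "comparisons will be made using two independent samples t-tests or Wilcoxon rank-sum tests", with no statement of whether the observations are students or schools. The one regression, of vaccination willingness on literacy, "will be analyzed using multivariate logistic regression", with no term for school. No mixed model, GEE, cluster-robust standard error or school-level analysis is named in any section.

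**The concern.** Chi-square and Fisher tests work on counts of independent individuals. Here the intervention is allocated to schools and delivered through school lectures, teachers and parent meetings, so students in one school are likely to resemble each other more than students in another. A test that treats roughly 1,400 students per arm as independent, when only ten schools per arm were randomised, understates the standard error. Ordinary variation between schools can then be declared an intervention effect. The vaccination rate is a primary outcome, and the results are meant to inform school officials and health departments.

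**Working it through.** **The plan's own figures.** 138 × 20 = 2760, and 2760 × 1.10 = 3036, as stated. The 138 itself cannot be reproduced, because the correlation, the cohort size and the adopted power are not given (0.8 is only an example). With zero correlation, 80% versus 50% and z = 1.96, the printed formula reduces to (1.96√2 + z_β)² × (0.16 + 0.25)/0.09:

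- 80% power (z_β = 0.84): 3.612² × 4.556 ≈ 59.
- 90% power (z_β = 1.28): 4.053² × 4.556 ≈ 75.

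Both are well below 138, so a non-zero correlation was most plausibly assumed.

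**Inputs for the error rate.** m = 138 (stated) or 152 (the per-school minimum; 3036/20 = 151.8); ten schools per arm, five per district; a two-sided 5% level, taken from the example beside the formula because the SAP states none. *Assumed:* a school ICC of 0.01 to 0.05, meaning the average correlation between two students of the same school; a share f of the between-school variance that is due to district; equal school sizes.

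**Formula.** The 5:5 split cancels district differences from the arm comparison, so the variance relative to independent students is

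D = m × ICC × (1 − f) + 1 − ICC,

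and the true size of the nominal 5% test is 2 × [1 − Φ(1.96/√D)].

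Worked case: m = 138, ICC 0.01, f = 0 gives D = 1.38 + 0.99 = 2.37, 1.96/√2.37 = 1.273, size 20.3%.

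| District share f | ICC 0.01, m = 138 | ICC 0.01, m = 152 | ICC 0.05, m = 138 | ICC 0.05, m = 152 |
|---|---|---|---|---|
| 0 | 20.3% | 21.6% | 48.4% | 50.3% |
| 0.50 | 13.0% | 13.8% | 35.0% | 36.9% |
| 0.75 | 9.0% | 9.4% | 23.1% | 24.6% |
| 1 | 4.9% | 4.9% | 4.4% | 4.4% |

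Beta-binomial simulation of the same design (40,000 runs per cell, null rate 50%) agreed with the formula within 0.7 percentage points.

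**What the test would call significant.** With m = 138 and a 50% rate, the independent-student standard error is √(0.5/1380) = 1.90 points.

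- Chi-square: 1.96 × 1.90 = 3.7 points.
- School-level test, 17 df (20 schools less three parameters), f = 0: 2.110 × 1.90 × √2.37 ≈ 6.2 points at ICC 0.01, and 2.110 × 1.90 × √7.85 ≈ 11.3 points at ICC 0.05.

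At these ICCs, with no district effect, a difference between 3.7 points and the school-level threshold would be declared significant only because clustering was ignored.

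**Does a valid test cost the trial its planned result?** Regression of school proportions on arm and district held its size at 4.8% to 5.3% in simulation (20,000 runs per setting). Its power for 80% versus 50% is above 99% at ICC up to 0.05.

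**The case against.** The best defence is that the introduction already makes the school the unit of analysis, so the SAP may be shorthand. That does not rescue the vaccination rate: chi-square and Fisher tests need counts of students and cannot be run on 20 school proportions. The defence has more force for the t-test and Wilcoxon sentence, which could be applied to school means. A reader might infer that literacy is certain to be tested at student level; the SAP does not say so.

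Four further objections limit the point, and they stand.

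- *District balance.* A reader might infer that any difference between schools breaks the test. It does not. District differences cancel under the 5:5 split; only differences within district inflate the error. The 9% lower figure is therefore no floor: at ICC 0.01 and m = 138, the size is 6.5% if district explains 90% of the between-school variance.
- *The planning ICC.* A reader might infer that 138 proves clustering was assumed and reveals its size. With correlation, cohort size and power all unstated, many combinations give 138: a cohort of 138 at 80% power needs 0.0096, a cohort of 38 needs 0.0355. No back-solved ICC should be relied on.
- *The planned effect.* A reader might infer that the main conclusion is in danger. If the true difference is near 30 points, a valid test finds it too.
- *The SPIRIT checklist.* Item 20b is marked not applicable, but it covers additional analyses. It does not show that clustering was ruled out for the primary comparison.

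**Conclusion.** The planned test of a primary outcome does not match the randomisation or the plan's own unit of analysis, and should be changed before analysis. If schools differ within district, it does not hold a nominal 5% error rate. How far it departs depends on an ICC that the documents do not give. For the assumed 0.01 to 0.05, with equal school sizes, the range runs from about 20% to 50% with no district effect down to 9% to 25% with a 75% district share. It is nominal only if schools within a district do not differ at all beyond chance, which nothing in the documents suggests. The practical risk lies in vaccination differences well short of 30 points, and in literacy, which has no stated effect size and no stated level of analysis. The contradiction itself is certain; the percentages are conditional.

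**What to change.** In the SAP, replace the unadjusted chi-square/Fisher comparison between arms with one pre-specified analysis that respects school and adjusts for district. One option is linear regression of the school vaccination proportion on arm and district (20 schools, 17 df), with the weighting of schools stated in advance. A mixed model or GEE with a small-sample correction is equally acceptable. Report the difference in percentage points, its 95% confidence interval and the ICC.

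Apply the same allowance to literacy and to the between-arm comparisons of influenza and ILI incidence. In the willingness regression, and in any inference on the vaccine protection rate, use school-clustered standard errors with a small-sample correction. These two are not arm comparisons, so the error rates above do not apply to them.

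The cost is SAP wording; the parent questionnaire already asks for school and street. P-values will be less favourable and intervals wider. With 138 per school and no district effect, power for a 10-point difference from 50% is about 90% at ICC 0.01 and 42% to 43% at ICC 0.05. For the planned 30 points it stays above 99%.

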Appendix

Appendix I Health Literacy Research Questionnaire (Parent Version)

Appendix II Health Literacy Research Questionnaire (Student Version)

Appendix III Registration Form of Influenza-like Cases in the School Clinic

Appendix IV SPIRIT 2013 Checklist

**Appendix I Questionnaire for the Health Literacy Study of Influenza Vaccination
among Primary School Students in Dongguan City (Parent Version)**

Question

Basic information

The street where your child's school belong is?

Your child's school?

Your child's ID type?

Your child's ID number?

Your phone number?

Are you the child's father, mother or?

Do you currently live with your children?

Your age?

Your spouse's age?

Your highest level of education?

Your spouse's highest level of education?

Your occupation?

Your spouse's occupation?

Your home address?

Your household income?

How many children do you currently have?

How is your child's health?

Knowledge questions

Do you know what the symptoms of flu are?

Do you know when is the flu season in Dongguan?

Do you know how the flu is transmitted?

Do you think the flu is an infectious disease?

Do you know what the flu vaccine is?

Have you heard of the flu vaccine?

Do you know the minimum age for children to receive their first

flu vaccination?

Do you think it's appropriate to get the flu vaccine during a flu epidemic?

Do you know the contraindications of flu vaccination?

Do you know what the possible side effects of the flu vaccine are?

Attitude Questions

Do you think the flu is just a cold?

Do you think you need to be quarantined at home after getting the flu?

Do you think your family and friends are likely to get the flu during the pandemic season?

If you or your child gets the flu, there is a high risk of transmitting it to others around you?

Do you think that getting the flu can cause serious consequences or complications?

If you or a family member gets the flu, it can have a serious impact on your or your family's health?

Do you think the flu vaccination is the most effective preventive measure against influenza?

Do you think the flu vaccination is effective in reducing the risk of spreading the influenza virus?

Do you think the flu vaccination will reduce the risk of your family getting the flu?

Do you think the flu vaccination will reduce the symptoms of influenza in your family?

Do you think children are a priority and recommended population for the flu vaccination?

Do you think the flu vaccine needs to be given every year to

prevent the flu?

Do you think getting a flu vaccine is good for you and your child's health?

Do you think it is necessary to get a flu vaccine?

Are you confident that the flu vaccine is safe?

Behavioral questions

Within the last year, have you ever had influenza (or had a sudden onset of illness with a high fever $\geq 38^{\circ}\text{C}$ accompanied by flu-like symptoms such as generalised malaise, myalgia, sore throat, etc.)?

If yes, when was the last time you had influenza (or had a sudden onset of illness with high fever $\geq 38^{\circ}\text{C}$ accompanied by influenza-like symptoms such as generalised malaise, myalgia, sore throat, etc.)?

Has your child had influenza (or had a sudden onset of illness with high fever $\geq 38^{\circ}\text{C}$, accompanied by flu-like symptoms such as generalised weakness, myalgia, sore throat, etc.) within the last year?

If yes, when was the last time your child had influenza (or had a sudden onset of illness with a high fever $\geq 38^{\circ}\text{C}$ accompanied by influenza-like symptoms such as generalised malaise, myalgia and sore throat)?

Have you taken your child for a flu vaccination between 2020 and 2022?

Have you or your spouse been vaccinated against flu in 2023?

If you have been vaccinated against flu, when did you or your spouse get the flu vaccine this year?

Has your child been vaccinated against flu in 2023?

If your child has been vaccinated against flu, when did your

child get the flu vaccine this year?

If your child has been vaccinated against flu, why did you decide to take your child for a flu vaccination this year?

If your child hasn't been vaccinated against flu, why did you decide not to take your child for a flu vaccination this year?

If your child has not had a flu vaccination this year, are you currently willing to take your child to get one?

Would you be willing to take your child for a flu vaccination in the future?

Would you like to recommend that others get the flu vaccine?

Skill Questions

Do you know how to schedule your flu vaccine?

Do you take an active interest in information about flu vaccinations?

Where do you get information about flu vaccinations?

Appendix II Questionnaire for Health Literacy Study of Influenza Vaccination among Primary School Students in Dongguan City (Student Version)

Question

Basic information

Your class?

Your gender?

How old are you?

knowledge questions

Have you heard of the influenza or flu?

Do you know what the symptoms of having the flu are?

Do you think you can spread the flu to other people when you get it?

Do you think you can go to class after getting the flu?

Have you heard of the flu vaccine?

Do you know what the flu vaccine does?

Do you know how the flu vaccine works? (For example, it helps our body learn how to beat the flu virus)

Attitude Questions

Do you think getting a flu vaccine is a good thing or a bad thing?

Are you afraid of getting the flu vaccine? Why?

Behavioral questions

Within the last year, have you had the flu (or had flu-like symptoms such as sudden high fever, temperature over 38°C, general lack of energy, headache, sore throat, etc.)?

If yes, when was the last time you had influenza (or had a sudden onset of illness with high fever $\geq 38^{\circ}\text{C}$ accompanied by influenza-like symptoms such as generalised malaise, myalgia, sore throat, etc.)?

Have you been vaccinated against flu in 2023?

If you have been vaccinated, when did you get your flu vaccine in 2023?

Would you like your parents to take you for a flu vaccination?

Skill Questions

Where do you get information about flu vaccinations?

Who do you ask if you have questions about the flu vaccine?

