Staff of the affiliated street Center for Disease Prevention and Control (CDC) will visit the school in the first month to implement intervention activities using the health education intervention package. The intervention period will commence in September 2023 and conclude in February 2024, resulting in a total intervention duration of approximately three to four months. The specific intervention process is as follows: 1) At the start of the semester (early intervention stage in September 2023), initiation activities will be conducted. The investigators will introduce the study to teachers and students, and medical professionals or public health experts will be invited to deliver classroom lectures at the intervention group schools. Baseline data will be collected at this stage. 2) During the intervention period (September 2023 – January 2024), the intervention group will follow the health education intervention toolkit to conduct intervention activities. 3) At the conclusion of the semester (February 2024), follow-up data will be collected. The intervention timeline is shown in the Figure 2.

Data collection and analysis

Questionnaire surveys will be administered to students and parents before and after

the intervention, using self-completion. The questionnaire design, which is informed by similar research literature (Appendix 1 & 2), will undergo evaluations for reliability and validity. The questionnaire will include the following content: 1) Socio-demographic characteristics (name, age, sex, class, residential address, parents' educational level, occupation, family income); 2) Personal history (basic disease history, allergy history, and personal history); 3) Influenza vaccination health literacy level. The health literacy level concerning influenza vaccination will be assessed across four dimensions: knowledge, attitude, behavior, and skills related to influenza vaccination. Details of these four dimensions include knowledge of basic facts about the influenza vaccine (such as its efficacy, vaccination frequency, and side effects), attitudes towards the influenza vaccine (including perceptions of its efficacy and safety), behavioral characteristics related to influenza vaccination (such as willingness to be vaccinated, vaccination status, and timing of vaccination), and sources of information about the influenza vaccine.

Confirmation of influenza and surveillance of influenza-like cases

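### The primary vaccination rate has no stated source or date window, and the only appended forms ask about calendar 2023 although follow-up is in February 2024

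*Combined protocol and SAP*

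**What the plan says.** All references are to the combined protocol and SAP.

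- *Study outcomes* makes the vaccination rate one of two primary outcomes: vaccinated children over all children, as a percentage. It names no data source, time point or date window.
- *Data collection and analysis* has students and parents complete questionnaires before and after the intervention. Vaccination status and timing are listed among the contents, under the behaviour dimension of health literacy. No separate follow-up version is described. The questionnaire is still to be evaluated for reliability and validity.
- *Intervention time* starts activities in September 2023 and runs them to January 2024. CDC staff "will visit the school in the first month to implement intervention activities". Then: "At the conclusion of the semester (February 2024), follow-up data will be collected".
- Appendix I (parent form) asks "Has your child been vaccinated against flu in 2023". Its date item, printed over two lines, reads "If your child has been vaccinated against flu, when did your" and "child get the flu vaccine this year".
- Appendix II (student form) asks "Have you been vaccinated against flu in 2023" and then "If you have been vaccinated, when did you get your flu vaccine in 2023".
- The SPIRIT checklist (Appendix IV), item 18a, points to Appendices I and II for the collection of outcome and baseline data.

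**The concern.** The questionnaire is the only documented source of vaccination status that covers both arms, and no register or clinic record is named. Its printed status items stop at 31 December 2023, while activities, including the vaccination service in the intervention package, continue into January 2024 and the survey follows in February. A first dose in those last weeks would be recorded as no vaccination. At the other end, the same items admit doses given before the trial began.

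A primary outcome is at stake. Vaccination status also defines the two groups compared in the vaccine protection rate, a secondary outcome, and it appears in the literacy questionnaire. With no source or window in *Study outcomes*, nothing in the plan overrides the printed wording, and nothing tells the analyst what to do with a dose dated outside the trial period.

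**Working it through.** **1. The plan's own contrast.** *Sampling method* assumes 80% in the intervention arm and 50% in the control arm: 0.80 − 0.50 = 0.30, or 30 points. These are taken as the true rates below.

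**2. Printed wording against the calendar, if the forms are completed in February 2024.**

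| Dose date | Days | Truthful answer to the status item | Within the trial period? |
|---|---|---|---|
| January–August 2023 | 243 | yes | no |
| September–December 2023 | 122 | yes | yes |
| January–February 2024 | 60 | no | yes |

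January is 31 of the 153 days from September to January (20%). January and February are 60 of the 182 days to the end of February (33%). These are shares of the calendar, not of doses.

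The parent date item depends only on the child having been vaccinated and refers to the current year, so it might capture a 2024 dose. It follows a question about 2023, however, and read in February 2024 the two disagree. The student date item is itself limited to 2023 and offers no such route.

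**3. Effect on the contrast.** Let f be an arm's share of doses given in January–February 2024, and r the share of those caught by the parent date item. Both are assumptions; the documents give neither.

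Measured rate = p × [1 − f × (1 − r)]

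| f, intervention | f, control | r | Measured rates | Difference (points) |
|---|---|---|---|---|
| 5% | 5% | 0 | 76% vs 47.5% | 28.5 |
| 10% | 10% | 0 | 72% vs 45% | 27 |
| 20% | 20% | 0 | 64% vs 40% | 24 |
| 10% | 10% | 0.5 | 76% vs 47.5% | 28.5 |
| 20% | 20% | 0.5 | 72% vs 45% | 27 |
| 10% | 5% | 0 | 72% vs 47.5% | 24.5 |
| 5% | 10% | 0 | 76% vs 45% | 31 |
| 5% | 8% | 0 | 76% vs 46% | 30 |

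The difference is 0.30 − (1 − r)(0.80 f₁ − 0.50 f₀), where f₁ is the intervention share and f₀ the control share. With r below 1, it shrinks when 0.80 f₁ exceeds 0.50 f₀, grows when it is less, and is unchanged when the two are equal, as in the last row.

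**4. Power, as a guide to materiality.** *Sampling method* gives no ICC value, so a range is assumed. Each arm has 10 × 138 = 1,380 children, and effective n per arm = 1,380 / (1 + 137 × ICC). Power is from the normal approximation for two proportions, two-sided 5%, with r = 0.

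| ICC (effective n) | No late doses | 20% late, both arms | 20% late, intervention arm only (64% vs 50%) |
|---|---|---|---|
| 0.05 (175.8) | over 99% | 99.6% | 75.7% |
| 0.10 (93.9) | 99.3% | 91.5% | 49.1% |
| 0.20 (48.6) | 88.5% | 66.3% | 28.4% |

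**5. Earlier doses.** *Intervention methods* opens the vaccination service to children four to six months after their last dose. Counted back from September 2023, that is March to May 2023. Such a child answers yes to the 2023 item whatever happens in the trial. The exclusion of recently vaccinated children in *Study sample* gives no interval, so it does not settle who remains. The baseline answer or the dose date could separate these doses, so they are not in the table in step 3; but no rule says that this will be done.

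**The case against.** The strongest reply is that the appended forms may simply be the baseline wording. The document is dated 1 September 2023, and the parent form's references to 2020–2022, to 2023 and to the current year fit together only if it is completed in 2023. The wording may also change after the reliability and validity evaluation. This stands in part: reuse in February is an inference. It remains a fair one, because a single questionnaire is described for both surveys and the checklist gives these appendices as the outcome forms. The silence of *Study outcomes* on source and window does not depend on it.

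Second, late doses may be few. CDC staff visit in the first month, and *Study design* and *Intervention time* both put the duration at three to four months. That also stands. The stated duration does not match the calendar dates given beside it (September to February), and the two need reconciling, since they bear on the window.

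Third, late doses might be recovered through the parent date item or the on-site re-testing under *Quality control*. They might, but neither is tied to correcting vaccination status. The forms appear as question stems only, so how dates are recorded cannot be judged.

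A reader might go further and infer that the trial will misclassify its primary outcome, that the effect will be diluted, or that power will be lost. The documents support none of these. Reuse is not stated, the direction depends on unequal late shares about which nothing is said, and the low power figures need both an assumed ICC and late doses concentrated in the intervention arm.

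**Conclusion.** The plan does not say where the primary vaccination rate comes from or which dates count, and the only forms it appends do not fit a February 2024 survey. That much is certain. Conditional on the printed wording being reused, a first dose in January–February 2024 is recorded as no, with uncertain rescue from the parent date item, and doses from January to August 2023 are counted.

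The size and direction of the bias are unknown and it may be small. Equal late shares of 5% to 20% would take the planned 30 points to between 28.5 and 24 if no late dose were recovered; unequal shares could move it either way. These figures rest on assumed late shares and on the planning rates being true. The point should be fixed because it touches a primary outcome and the remedy is cheap, not because a material bias has been shown.

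**What to change.** **Follow-up forms.** In both, replace the calendar-year and current-year wording with one fixed window, from the start of the intervention term in September 2023 to the day of the survey, and record the dose date. The window should open at the start of term and not at the baseline survey, because *Intervention time* puts baseline collection in the same stage as the launch lectures, and an early September dose could otherwise be labelled as preceding the trial.

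***Study outcomes*.** Add two or three sentences that:

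- name the parent questionnaire as the source in both arms, linked across surveys by the child's ID number, which the parent form already collects;
- state the same window;
- give one rule, identical in both arms and fixed before follow-up data are seen, for doses dated before the window. Whether such a child counts as vaccinated, stays in the denominator as not newly vaccinated, or is left out is the authors' choice of estimand.

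**Student answer.** Use it as a child-level check only if the student form carries an identifier; as printed it asks only class, gender and age. Otherwise compare at class level. The printed parent form asks for the school but not the class, so the class would have to be added or looked up.

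**Cost.** A few reworded items and a short addition to the text before February 2024, with no extra visits or staff. The downside is slightly different wording between the baseline and follow-up forms.
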